1.2 Study organization

The study will be fielded at the Thanh Hoa Provincial Centre of Reproductive Health in Vietnam. Testing for prostate-specific antigen (PSA) will be conducted at the Microbiology and Human Challenge Core Laboratories of the UNC Sexually Transmitted Diseases Cooperative Research Center (STD-CRC) in Chapel Hill, NC, US. Data management will occur through collaboration between the field site and OSU. The Site Investigator will manage the daily trial operation. Key staff will employ regular communication by telephone (occurring weekly during study start-up and initiation and then decreasing to a monthly basis unless needed more often), and the Principal Investigator (PI) or designee will perform on-site monitoring at pre-initiation, during study implementation (occurring annually or more often, if needed), and at study close-out.

1.3 Ethical review

Ethical oversight for the research will be provided by The OSU Biomedical Institutional Review Board (IRB), which is registered with the Office of Human Research Protections and covered by a Federal Wide Assurance (FWA00006378), and the Hanoi University of Public Health Biomedical IRB (FWA00009326). UNC-Chapel Hill will defer their review of the protocol to the OSU IRB.

2. STUDY SUMMARY

This randomized controlled trial will test whether promoting the novel condom CSD500 (Futura Medical Developments; Surrey, UK) for improved sexual pleasure results in couples having less unprotected vaginal sex – measured with a biological marker of recent semen exposure – compared to the promotion of a standard condom for disease and pregnancy prevention. CSD500 contains an erectogenic drug and was developed to improve sexual pleasure by increasing penile firmness, size, and erection duration.

We will recruit eligible, monogamous, heterosexual couples at Thanh Hoa Provincial Centre of Reproductive Health in Vietnam to participate in a randomized controlled trial (RCT) of two balanced arms of approximately 250 couples each. At enrollment and at three follow-up visits scheduled at 2, 4 and 6 months after enrollment, we will provide condom counseling, will collect double-headed vaginal swabs to test for the semen biomarker, prostate-specific antigen (PSA), and will administer a questionnaire to the female participants on their demographics, sexual and condom-related attitudes and practices, including sexual pleasure and perceptions of partner's sexual pleasure. Although the intervention is directed to the women, couples will be enrolled to ensure that the male partners consent to CSD500 use. After enrollment, male participants will not participate in study visit activities, including data collection, until the time of their female partner's final 6-month visit. Because of the differences in counseling messages, participants and study staff at the site cannot be blinded to arm assignment.

Primary aims:

1. To evaluate whether CSD500 provided to improve sexual pleasure, as compared to the standard condom, results in less semen exposure among women in an established relationship
2. To evaluate the effects of CSD500 provision on men and women's reports of sexual pleasure compared to the standard condom
3. To identify correlates of semen exposure measured by PSA positivity

Study design: RCT with two arms: CSD500 for sexual pleasure or the standard condom currently provided for pregnancy and disease prevention

Study site: Thanh Hoa Provincial Centre of Reproductive Health

Data collection: Women: questionnaires and vaginal swabs for PSA testing at enrollment and the 2, 4, and 6-month visits
Men: questionnaires at enrollment and the 6-month visit

Sample size: ~500 couples with balanced assignment to the two study arms

Study population: Adult, monogamous, heterosexual couples willing to use the assigned condoms and who at enrollment are not using – or intending to start in the next 6 months – a modern contraceptive method other than condoms

Data analysis: Intent-to-treat analysis

3. STUDY PRODUCT: CSD500

CSD500 is a commercial condom that complies fully with the requirements of ISO 4074, the international standard for male latex condoms. The 53 mm-width, latex condom is transparent with a teat at the end containing a pharmacological dose of Zanifil™ (active ingredient glyceryl trinitrate 1% w/w). The product works by increasing blood flow, which helps to maximize erection hardness.

CSD500 has been approved for over-the-counter use in 27 European nations and is being sold under the name “*Blue Diamond*™” in The Netherlands and Belgium but has not been registered in the U.S. or Vietnam. They will be labeled with the brand name “Futura Max” in the present trial. We will meet NIH requirements for regulatory oversight (see <http://www.niaid.nih.gov/researchfunding/sci/human/pages/hshandbook.aspx>) by obtaining regulatory approval from the Vietnam MOH to use the product solely for research purposes in compliance with local laws (see letter from [name]). Futura Medical Developments has agreed to provide CSD500 for the study at no cost without having any other role or influence (see letter from [name]). To maximize sales and improve adherence to condom use, the manufacturer recommends that its distribution partners use a target price that is, at most, 50% more than current condom prices ([name], written communication, August 2014). CSD500 is expected to be widely available in settings worldwide, and its access is unlikely to be limited by price given its modest premium compared to standard male condoms.

Two industry-sponsored trials have assessed the effects of CSD500 on user performance and pleasure. The first was a randomized crossover trial conducted among 120 healthy, heterosexual couples recruited from a clinic in London, England who reported being in stable relationships of ≥ 6 months and in which the male partner reported ≥ 1 partial or total loss of penile tumescence during condom use in the past six months ([name], written communication, August 2014). Couples were randomly assigned to use CSD500 or standard condoms for five acts followed by five uses of the other condom type. Both the man and woman independently completed a diary for each condom use. Females perceived an increase in penile firmness ($p<0.01$), an increase in penis size ($p=0.07$), and erections of longer duration ($p=0.04$) with CSD500 relative to the standard condom. Men also reported increased penis size ($p<0.01$) and erections of longer duration ($p=0.02$) with CSD500 compared to the standard condom. The second was a single-arm trial of CSD500 among heterosexual men (N=91) and women (N=38) in Argentina. Both men (54%) and women (63%) reported that the condom improved sexual performance, with participants citing improved sensations, comfort, texture, erection duration and confidence ([name], written communication, January 2015).

4. RATIONALE

Promoting a novel condom designed to improve sexual pleasure could lead to less unprotected sex and, thereby, reduce the risks of both unintended pregnancy and HIV/STI.

As the sole method for dual protection against pregnancy and HIV/STI, condoms play an important role in public health. Male condoms protect against pregnancy (Trussell 2011) and the transmission of HIV, chlamydia, gonorrhea, trichomoniasis, herpes simplex virus type 2, and syphilis (Holmes 2004; Weller 2002). Given their effectiveness against both pregnancy and disease when used consistently and correctly, condoms alone (rather than with another modern method) have been recommended for those needing dual protection (O’Leary 2011). Condoms have many positive attributes: low cost, availability without a prescription, minimal side effects, few contraindications, and global presence. Sustained use, however, is notoriously difficult to achieve. Only 9% of reproductive-age women in the U.S. in 2011-2013 reported current condom

use (Daniels 2014). Similarly, a national survey in Vietnam found that only 9% and 7% of sexually-active, married, reproductive-age women reported condom use at last sex act and consistent condom use, respectively (Do 2011). Substantial unmet need for contraception, partly stemming from concerns about safety of hormonal contraception, drives Vietnam's high abortion rate. Married women account for about one-third of HIV cases in Vietnam (MOH 2009), and among this group, most were exposed to the virus through sexual activity with their husband (UNAIDS 2010; Nguyen 2008). **Thus, increasing condom use within established partnerships is crucial for preventing HIV/STIs while also protecting women against unintended pregnancy.**

A range of condom-related factors can diminish sexual pleasure: physical effects, including dulled sensation, pain, discomfort, or vaginal dryness (possibly from inadequate condom lubrication); unappealing perception of the touch, taste, or smell of condoms; lack of spontaneity or interruption to the flow of sex; and social constructs (e.g., decreased emotional closeness or inability to express male vitality by ejaculating into the vagina) (Hensel 2012; Sanders 2014). **Dulled sensation can lead to erection loss: an estimated 9%-37% of condoms users have had erection problems during condom application or use** (Graham 2006; Sanders 2012; Sanders 2014). This experience – especially during initial, formative sexual encounters – has been shown to make some men less confident about their ability to maintain an erection during condom use, which may then cause a negative feedback loop of erectile dysfunction (Sanders 2014). Condom-related erection loss also could dissuade men from future attempts to use a condom.

A national survey in Vietnam found that despite widespread lack of personal experience with the device, about 70% of youth believed that condoms reduce sexual pleasure (MOH 2005). This finding is consistent with a 14-country study identifying diminished sexual pleasure as the primary objection to condom use (Mehryar 1995) and with a large U.S. study, in which 31% of heterosexual male and female users of condoms reported a problem with the feel of the device (Crosby 2013). Although the physical properties of condoms directly affect men, women can be even more resistant toward condom use possibly, in part, from weighing their male partner's pleasure as an important contributor toward their own pleasure (Higgins 2008). Women also might be reluctant to require condom use because of concerns that this will lead to their partner seeking unprotected sex elsewhere. Perceptions about condom effects on sexual pleasure and arousal are important because they are directly related to frequency of actual use (Crosby 2013; Higgins 2009; Randolph 2007). While the effectiveness of structural and community-level interventions for increasing condom use remains unclear (Moreno 2014), individual counseling has been shown to reduce STI incidence among adolescent and high-risk adult populations (Lin 2008). Less research has focused on heterosexual couples in purportedly monogamous relationships.

Increasingly, the importance of sexual pleasure has been recognized for informing interventions on safer sex. Condoms have been modified in terms of their size, taste, appearance, texture, smell and thickness to improve the user experience (Cecil 2010; Crosby 2010). Eroticizing the protection afforded by condoms appears to be a successful strategy employed by consistent condom users in Mexico and the Dominican Republic (García 2003; García 2004). Other interventions have included selling condoms packaged with water-based lubricant sachets as pleasure enhancements in Cambodia and socially-marketing textured male condoms in Uganda (Philpott 2006). Increased sales of these products suggest that interventions to improve sexual pleasure with condoms can increase frequency of condom use.

5. PSA OUTCOME

The primary study endpoint, detection of PSA in vaginal fluid, is a feasible marker of women's recent exposure to semen from penile-vaginal sex. Forensic research demonstrates that PSA clears from the vagina in a mean of 20-27 hours and is undetectable after 47 hours (Graves 1985; Kamenev 1989). More recently, the protein has been studied for its potential as a semen biomarker for research purposes. Three studies using a controlled design in which women were exposed to specific quantities of their partner's semen in a clinic setting showed high proportions of women tested PSA-positive immediately after exposure (Lawson 1998) followed by a sharp decay curve (Macaluso 1999; Jamshidi 2013). For example, when women were exposed to 1 mL of semen (a volume on the same order of magnitude as the amount in a typical ejaculate) (Cooper 2010), Macaluso et al. found PSA (>1 ng/mL) in 92%, 29% and 3% of women immediately, 24 hours, and 48 hours afterwards, respectively (Macaluso 1999). Given this pattern of clearance from vaginal fluid, observed PSA positivity should be interpreted as the lower bounds of exposure in the past 48 hours. PSA is stable in specimens stored at -70°C after collection (Gallo 2013a). Because it is expressed independently of spermatozoa, PSA is useful for identifying exposure even from men who are vasectomized or otherwise without high levels of spermatozoa. False positive PSA tests from women's endogenous sources of PSA (e.g., serum or urine) are improbable given that the resulting PSA levels would be several orders of magnitude below the established threshold for defining PSA positivity from semen exposure (Gallo 2013b).

To compare condom use between randomization arms, we will sample three short periods of exposure during follow-up (at 2, 4 and 6 months). Studies relying on self-reports of sex and condom use have a similar limitation in that they rarely attempt comprehensive measurement of condom use throughout study follow up. These studies typically ask about condom use at last sex act or, less often, over a short recent period to minimize potential for recall bias. The study will be powered to detect differences in semen exposure between the groups using this sampling. **Biomarkers provide an unbiased comparison of the frequency of semen exposure between randomized arms. In contrast, studies that rely on participant reports of exposure can be biased; the validity of reports vary by numerous study and participant factors, including HIV risk (Gallo 2011), which can result in confounding that cannot be addressed adequately in the analysis.**

We previously demonstrated in an RCT that advance knowledge of testing for PSA did not change women's behavior with respect to semen exposure or reporting of this behavior (Thomsen 2007). Thus, the act of consenting to study procedures, including sampling vaginal fluid to test for PSA, is not expected to influence participant behavior.

Preliminary data from an *in vitro* experiment conducted at the UNC laboratory provide evidence that the CSD500 condom does not interfere with the detection of PSA ([name], written communication, August 2014). Laboratory technicians spiked condom extracts (including material from the inside only, outside only, or a combination of both) and non-condom controls consisting of phosphate buffered saline (PBS) only with three concentrations of PSA (0.25, 2.00 and 11.50 ng/mL) and no PSA (control). Five independent samples of each condom extract condition were prepared for a total of 60 specimens and the PBS controls. Table 1 shows the mean PSA detected for each condition, which were all within manufacturer ranges.

Table 1. Detection of PSA in PBS alone or material extracted from the inside or outside of CSD500 condoms from spiked specimens, by PSA concentrations used for spiking

Spiked PSA concentration (ng/mL)	Architect Total PSA result (mean +/- standard deviation in ng/mL) for specimens prepared with ^a			
	PBS	Condom inside	Condom outside	Condom in/out
0.00	0.00 +/- 0.00	0.00 +/- 0.00	0.00 +/- 0.00	0.00 +/- 0.00
0.25	0.23 +/- 0.01	0.23 +/- 0.01	0.22 +/- 0.01	0.22 +/- 0.01
2.00	1.88 +/- 0.03	1.88 +/- 0.08	1.89 +/- 0.07	1.95 +/- 0.12
11.50	11.74 +/- 0.29	11.76 +/- 0.59	11.71 +/- 0.59	12.08 +/- 0.31

^aEach of the 16 test conditions (spiked PSA concentration by PBS or condom extract) evaluated for 5 independent specimens
PBS = phosphate buffered saline; PSA = prostate-specific antigen

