Aho 2010	Guinea	Sex workers	219	84	(38.4)
Anderson 2013	Jamaica	Syndromic STI patients	285 at day 0	24	(8.4)
			286 at day 6	29	(10.1)
Rattray [in press] ^a	Jamaica	HIV-negative, seeking contraception	414 at month 0	103	(24.9)
			401 at month 1	93	(23.2)
			389 at month 3	95	(24.4)
Gallo 2007	Kenya	Sex workers	194 at month 0	30	(15.5)
			183 at month 12	21	(11.8)
Mose 2013	Kenya	In a HIV-discordant relationship	124	3	(10.5)
Gallo 2006	Madagascar	Sex workers	332	126	(38.0)
Minnis 2009^a	Zimbabwe	Sexually-active, HIV-negative	910	196	(21.5)

^a*Two trials of HIV-negative women who were not sex workers or syndromic STI patients*

sizes to account for attrition. Specifically, we assumed that 10% would fail to return after enrollment and, among the 90% remaining in the study, the probability of missing a follow-up visit would be 25%.

Given these assumptions, 500 subjects split equally in two arms will provide us with adequate power (80% for all assumed ranges of values and 90% in many) to detect a clinically meaningful reduction in PSA positivity for most values of rho. For example, at the estimated rho of 0.23, this sample size yields 80% power to detect a RR of approximately 0.61 at alpha level of 0.05. Thus, a total sample of 500 women will ensure adequate power to detect a clinically meaningful change in the frequency of PSA positivity between the study arms.

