- Condom should be put on before the penis comes near or is put into the vagina.

5. **Demonstrates** how to correctly put on condom by using a model, banana, or two fingers.

- Cautions **not to unroll** condom before putting on.
- Shows how to place condom rim on penis and how to unroll up to penis base.
- Instructs on how to leave 1/2 inch space for semen at tip of condom, which must not be filled with air or it may burst.
- Shows how to expel air by pinching tip of condom as it is put on.
- Cautions about tearing accidentally with fingernails or rings.

6. Counsels about what to do if condom breaks or slips off during sex.

- Woman should return to clinic to be assessed for emergency contraception.
- Woman should request emergency contraceptive pills within 72 hours (the earlier the better) of unprotected sex or breakage of a condom.

7. Has patient demonstrate and practice putting on condom using the model, banana or fingers.

- Corrects any technique errors.

8. Counsels patient on how to remove penis from vagina with condom intact and without spilling semen.

- Hold on to rim of condom when withdrawing.

- Be careful not to let semen spill into vagina when penis is flaccid.

9. Discusses use of lubricants and what not to use.

- Do not use any of these: petroleum-based products (e.g., Vaseline); mineral, vegetable, or cooking oil; baby oil; margarine or butter.

10. Advises to use a spermicide or water-based lubricant if one is needed.

11. Advises patient to dispose of condoms by burning, burying, or throwing in the latrine.

12. Repeats main condom messages to patient.

- Be sure to have condom on hand before you need it.
- Use a condom with every act of intercourse.
- Do not use a single condom more than once.
- Do not rely on condom if package is damaged, torn, outdated, dry, brittle or sticky.

13. Provides patient with condoms for two months.

- Multiply patient's expected weekly coital frequency by 9. Give her this number of condoms or, if this number is less than 20, give her 20 condoms.

14. Instructs patient not to share study condoms with anyone but main partner.

- Do not share study condoms with family or friends.

15. Reassures patient that should return at any time for advice or more condoms.

VN CSD500 Study
Counseling Checklist: Intervention Arm

1. Greets patient respectfully.

- Assures privacy.
- Tries to put at ease if shy or embarrassed.

2. Asks what patient knows about condoms and about past experience with condoms.

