- Corrects any technique errors.

8. Counsels patient on how to remove penis from vagina with condom intact and without spilling semen.

- Hold on to rim of condom when withdrawing.
- Be careful not to let semen spill into vagina when penis is flaccid.

9. Discusses use of lubricants and what not to use.

- Do not use any of these: petroleum-based products (e.g., Vaseline); mineral, vegetable, or cooking oil; baby oil; margarine or butter.

10. Advises to use a spermicide or water-based lubricant if one is needed.

11. Advises patient to dispose of condoms by burning, burying, or throwing in the latrine.

12. Repeats main condom messages to patient.

- Be sure to have condom on hand before you need it.
- Use a condom with every act of intercourse.
- Do not use a single condom more than once.
- Do not rely on condom if package is damaged, torn, outdated, dry, brittle or sticky.
- **Futura Max condoms are designed to make sex more fun for the couple. Futura Max condoms contain a special gel that makes the man's erection get harder and last longer. This can make sex more pleasurable for the couple.**

13. Provides patient with condoms for two months.

- Multiply patient's expected weekly coital frequency by 9. Give this number of condoms or, if this number is less than 20, give 20 condoms.
- Give 2 standard condoms to use in case the couple has sex more than once within 24 hours.

14. Instructs patient not to share study condoms with anyone but main partner.

- Do not share study condoms with family or friends.

15. Reassures patient that should return at any time for advice or more condoms.

[figure not shown]
VN CSD500 Study
Futura Max™ Information Sheet

Futura Max™ condoms are natural rubber latex condoms which contain Zanifil® gel. They have been shown to maximize hardness by stimulating blood flow within the penis. This can help prevent loss or partial loss of erection, ensuring an intense experience for both you and your partner.

How to use: Use a condom only once. Condoms used more than once are more likely to slip or break and not provide adequate protection. Infections can be passed on in bodily fluids present in the condom after use.

1. Tear open the foil and remove the condom. Be careful with sharp objects such as nails and jewelry. If the carton or foil is damaged, discard and use a condom from an undamaged package.

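### Every follow-up PSA swab falls in the last two days of a condom supply interval, and above about 2.2 acts per week the supply rule leaves only about two days' reserve; supply should be increased and run-out recorded by arm

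*Combined protocol and SAP*

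**What the plan says.** Section 5 (PSA Outcome) sets the sampling: "we will sample three short periods of exposure during follow-up (at 2, 4 and 6 months"). On what one swab shows, it says "observed PSA positivity should be interpreted as the lower bounds of exposure in the past 48 hours".

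Sections 8.2 and 8.3 have condoms handed out at enrollment and at the 2- and 4-month visits. The amount is set in item 13 of each Counseling Checklist (section 16). Both say "Multiply patient's expected weekly coital frequency by 9", with a floor; the control version reads "if this number is less than 20, give her 20 condoms". The intervention checklist adds 2 standard condoms for a second act within 24 hours; the control checklist has no such line. Section 8.3 gives 20 condoms, or more according to expected frequency, without naming the multiplier.

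Item 15 of both checklists invites the woman back at any time for more condoms, and the Schedule of study procedures marks condom provision at interim visits as if needed. The same schedule marks no compensation for interim visits.

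Section 9.1 allows for missed visits: after 10% are lost post-enrollment, "the probability of missing a follow-up visit would be 25" percent. The note to its sample-size figure says instead that 25% of the remainder miss one visit.

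The plan states no coital frequency and no visit window in days. It describes no measure of running out. The questionnaires are listed but not reproduced, so such an item may exist there.

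**The concern.** The endpoint is read when the scheduled stock is lowest. A couple that never uses condoms cannot run out; a couple that uses one at every act can. If CSD500 promotion works, its arm contains more such couples, so run-out adds semen exposure that reflects the supply rule rather than the condom's acceptability. That would usually pull a true benefit toward RR 1 and cost power. Randomization and an objective biomarker do not remove it, because the exposure is real. Without a record of run-out, a null result could not separate a failed promotion from an exhausted supply.

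**Working it through.** **Plan's own figures.** The plan gives no reserve or run-out figure to reproduce. Section 9.1 states 80% power at RR 0.61 (control 0.15, rho 0.23, 250 per arm). With no attrition, effective n per arm = 250 × 3/(1 + 2 × 0.23) = 513.7, SE(log RR) = √[(0.85/0.15 + 0.9085/0.0915)/513.7] = 0.174, and power = 81%. With the plan's attrition it is 69% to 75%. This point does not rest on that gap, but power below is with attrition.

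**Reserve.** Two months = 365.25/6 = 60.9 days = 8.70 weeks. 9/8.70 − 1 = 3.5%, or 63 − 60.9 = 2.1 days. The 20-condom floor binds below 20/9 = 2.2 acts/week. The reserve is 20/17.4 − 1 = 15% at 2/week, 53% at 1.5 and 130% at 1.

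**Run-out before the swab window, first interval.** Assumptions: Poisson acts at the stated frequency f, a condom at every act, no resupply, the 2 extra condoms usable for any act. Mean acts before the last 48 hours = f × (8.70 − 0.29). Run-out = P(acts ≥ supply), with supply = max(20, 9f), plus 2 in the intervention arm. Control / intervention:

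| Acts/week | On time | One week late |
|---|---|---|
| 1.5 | 3% / 1% | 8% / 3% |
| 2 | 25% / 13% | 42% / 26% |
| 3 | 39% / 25% | 62% / 47% |
| 4 | 37% / 25% | 63% / 50% |

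After a missed visit, one supply must last four months: 89% / 79% at 1.5/week and about 99% or more at 2/week, with no leftovers.

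**Carry-over.** If leftovers are kept, simulated on-time run-out at months 2, 4 and 6 is 25, 12, 7% (control) and 13, 4, 1% (intervention) at 2/week. At 3/week it is 39, 26, 20% and 25, 13, 8%.

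**PSA positivity without condoms.** Section 5 cites detection of 92%, 29% and 3% at 0, 24 and 48 hours after 1 mL of semen. Log-linear interpolation gives 15.85 detectable hours per act. P(positive) = 1 − exp(−f × 15.85/168) = 17% at 2/week, 25% at 3 and 31% at 4.

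**Effect on the RR.** Assumptions: 25% (control) and 55% (intervention) of couples use a condom at every act and are otherwise PSA-negative; the rest are 20% positive. Then 0.75 × 0.20 = 0.15 and 0.45 × 0.20 = 0.09, RR 0.60. Half of run-out couples find replacements. Added positivity s = mean run-out over three visits × 0.5 × P(positive), and RR = (0.09 + 0.55 s_I)/(0.15 + 0.25 s_C).

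On time, with carry-over:
- 2/week: s_C 0.0127, s_I 0.0052; 0.0929/0.1532 = 0.61
- 3/week: s_C 0.0348, s_I 0.0187; 0.1003/0.1587 = 0.63
- 4/week: s_C 0.0409, s_I 0.0237; 0.1030/0.1602 = 0.64

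Same model, less favorable attendance:
- every visit one week late: 0.62, 0.69 and 0.73 at 2, 3 and 4/week
- 25% of women miss one visit: 0.62, 0.65 and 0.67
- each visit missed with probability 25%: 0.64, 0.68 and 0.71

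**Power.** With n = 225 per arm (250 × 0.9), m = 2.25 visits (3 × 0.75) or 2.75 (0.75 × 3 + 0.25 × 2), and rho 0.23, power is 72% to 77% at RR 0.60. On time with carry-over it is 72% to 77% at 2/week, 67% to 72% at 3 and 65% to 70% at 4. With every visit a week late it is 69% to 74%, 55% to 59% and 45% to 49%.

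**No true effect.** With 25% every-act users in both arms, on time at 3/week: (0.15 + 0.25 × 0.0187)/(0.15 + 0.25 × 0.0348) = 0.1547/0.1587 = 0.97. A harsher case lets 39% of control and 25% of intervention visits be run-out visits at 25% positivity: (0.15 × 0.75 + 0.25 × 0.25)/(0.15 × 0.61 + 0.39 × 0.25) = 0.175/0.189 = 0.93.

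**The case against.** The strongest reply is that running out of the scheduled allotment is not the same as having no condoms. Resupply on demand is in both checklists and the schedule. The 20-condom floor protects couples at 1.5 acts per week or fewer when visits are on time. Nothing says leftovers are collected, so later visits start with more stock. The calculation also needs a condom at every act: at 80% use, average control run-out over the three visits is about 2% at 2/week and 4% at 3/week. Section 4 cites 7% consistent condom use among married Vietnamese women. All of this stands and limits the size. It does not remove the timing, the two-day reserve for more active couples, or the absence of any stated run-out record. Resupply also takes an extra trip without scheduled compensation.

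A reader might infer more: that couples are often without condoms at the swab, or that power falls below one half with on-time visits. The documents do not support this. They give no coital frequency, and in these calculations power below one half arises only at 4/week with every visit a week late.

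A reader might also infer that the intervention arm is worse supplied because CSD500 "has not been registered in the U.S. or Vietnam". That does not follow. PSA detects semen, not condom brand; intervention couples can use standard condoms and receive 2 extra, so at a given frequency their modeled run-out is lower than in the control arm.

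**Conclusion.** The point holds as a conditional weakness of the supply rule. The swab timing and the 3.5% reserve above about 2.2 acts per week follow directly from the documents. At 2 to 4 acts per week, a true RR of 0.60 would be seen as about 0.61 to 0.64 with on-time visits and carry-over, and about 0.62 to 0.73 with late or missed visits. Coital frequency, the adherence mix, the half-replacement share, the Poisson model and retention of leftovers are assumptions; actual use of on-demand resupply would reduce the effect. If a true benefit exists, the modeled direction is toward 1. If none exists, the unequal extra condoms could move the RR slightly below 1, so the direction is not guaranteed. This is a worthwhile low-cost improvement, not a flaw that invalidates the primary comparison.

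**What to change.** In item 13 of both Counseling Checklists, replace the nine-week multiplier with a larger one, identical in both arms, that covers the scheduled visit date plus the lateness the site will tolerate. The sponsor sets the figure. State the same rule in section 8.3, and leave the instructions for use unchanged.

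Add one item to the Female Follow-up Questionnaire, asked before resupply: had the couple run out of study condoms since the last visit, and if so when? Report the answers by arm and visit beside the primary RR.

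The cost is more condoms for couples above roughly 2 acts per week (CSD500 is supplied to the study at no cost, and the standard condom is free under usual care), some left over, and one extra question.
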